## **JHM IRB - eForm A – Protocol**

### **1) Abstract**

The treatment of hydrocephalus is the most time-consuming, and arguably the most important, role of the pediatric neurosurgical service at most childrens' hospitals. Despite many technological advances, cerebrospinal fluid (CSF) shunting procedures remain the mainstay of hydrocephalus treatment. While often lifesaving, CSF shunting procedures are associated with high complication rates and account for a disproportionate share of health care expenditures and morbidity.

Programmable CSF shunt valves, through which CSF flow and pressure can be adjusted by quick and painless transcutaneous reprogramming, have been implanted for more than 15 years in the developed world. Reprogramming these valves relies on rotational magnetic forces, which are easily and painlessly applied by neurosurgeons and neurosurgical advanced practice providers. Inadvertent reprogramming (IR) can occur when patients with these valves are exposed to magnetic fields in their environment, which may lead to serious symptoms that may require urgent reprogramming and/or surgery.

The concurrent proliferation of magnetically sensitive programmable CSF shunt valves and household items that generate substantial magnetic fields has caused concern among patients, parents and providers about the potential consequences of inadvertent valve reprogramming. This growing concern led the FDA in 2014 to issue a warning to individuals with programmable valves, which deemed programmable valves safe for use but vulnerable to IR when household devices such as tablets or cell phones are placed within 2 inches of them. The FDA recommended further study, stating that no systematic evaluation had been performed regarding the prevalence of accidental valve adjustments and the implications thereof.

By evaluating each of our patients with magnetically susceptible CSF shunt valves, during each of their routine points of contact with our service, we aim to define the prevalence of inadvertent shunt reprogramming, to correlate IR with the presence or absence of symptoms and radiographic changes, and to evaluate the risk of inadvertent shunt reprogramming based on exposure to common environmental items.

### **2) Objectives**

We intend to evaluate all patients 21 years old and younger with magnetically susceptible CSF shunts, specifically those with Strata (Medtronic, Dublin) valves implanted. All evaluations will be performed during routine patient

Date: 4/19/2016 V.2  
Principal Investigator: [name]  
Application Number: IRB00093490

## JHM IRB - eForm A - Protocol

care in the hospital, the emergency department and in our outpatient facilities. Valve settings will be checked transcutaneously in the standard manner, before and after any MRI studies. Our specific aims are:

- a. Aim #1: For hydrocephalic children with Strata CSF shunt valves, what is the frequency with which their valves have had inadvertent reprogramming (IR)?
- b. Aim #2: For hydrocephalic children with Strata CSF shunt valves, does the field strength of MRI scanning correlate with the likelihood that the shunt valve will change during the MRI study?
  - i. Hypothesis 2a: Exposure to 3T MRI will cause inadvertent Strata valve reprogramming more often than 1.5T MRI
- c. Aim #3: For hydrocephalic children with Strata CSF shunt valves, are patients who have had their valve inadvertently reprogrammed more likely to have signs, symptoms or radiographic changes suggestive of shunt malfunction than patients who have not?
  - i. Hypothesis 3a: Patients with Strata valve IR will be more likely to have clinical signs or symptoms of shunt malfunction than patients who have not had IR.
  - ii. Hypothesis 3b: Patients with Strata valve IR will be more likely to have radiographic findings of shunt malfunction than those who have not had IR.
- d. Aim #4: For hydrocephalic children with Strata CSF shunt valves, are patients exposed to devices that may have sufficient electromagnetic charge to affect programmable valves more likely to have their CSF shunt devices inadvertently reprogrammed by these devices than patients not exposed to those devices?
  - i. Hypothesis 4a: Patients with Strata valve IR will be more likely to have been exposed to household items that have been previously shown to electromagnetically affect shunt valve settings in vitro than those who have not had IR.
  - ii. Hypothesis 4b: Patients with Strata valve IR will have been exposed more frequently to household items that have been previously shown to electromagnetically affect shunt valve settings in vivo than those who have not had IR.
  - iii. Hypothesis 4c: Patients with Strata valve IR will be more likely to have had their shunt valve within 2 inches of

Date: 4/19/2016 V.2  
Principal Investigator: [name]  
Application Number: IRB00093490

## **JHM IRB - eForm A – Protocol**

electromagnetically charged devices than those who have had the devices placed farther from the valve.

### **3) Background**

#### *Scope of the Problem: Hydrocephalus*

The treatment of hydrocephalus in the United States has been estimated to account for \$1 billion in annual health care costs. Hospital care for children with hydrocephalus in the U.S. accounts for nearly 40,000 admissions per year, resulting in over 400,000 hospital days per year. The hospitalization costs for the care of preterm infants with post-hemorrhagic hydrocephalus alone average nearly \$500,000 per patient in the U.S.

While the treatment of hydrocephalus in children accounts for only 0.5% of hospital admissions in the US, it accounts for 1.8% of all hospital days and 3% of all hospital charges in pediatric facilities. Even though the treatment of hydrocephalus is critical to long-term quality of life and requires resources disproportional to its prevalence, NIH funding for hydrocephalus research is relatively low compared to funding provided for other medical conditions with a similar health care burden.

#### *Hydrocephalus Treatment*

Pediatric hydrocephalus is caused by numerous etiologies ranging from congenital malformations, hemorrhage related to prematurity, infection, brain tumor, trauma, spina bifida and other nervous system anomalies. Hydrocephalus can resolve without cerebrospinal fluid (CSF) diversion in some cases, such as when a brain tumor is resected or minor hemorrhage resolves in a premature infant. However, CSF diversion of some sort is usually required in the majority of pediatric patients with hydrocephalus.

Surgeons have performed CSF diversionary procedures for over 100 years, diverting flow from brain or spinal CSF spaces to a different organ space. Early efforts to divert CSF were met with frequent complications, primarily related to the implantation of a mechanical foreign body that was particularly prone to infection, occlusion and over drainage. Technological advances have vastly broadened the options available to surgeons, with resulting improvements in patient outcome. Most notably, the advancement of endoscopic techniques has allowed surgeons to

Date: 4/19/2016 V.2  
Principal Investigator: [name]  
Application Number: IRB00093490

## **JHM IRB - eForm A - Protocol**

create internal CSF diversionary pathways, which can eliminate the reliance on an implanted mechanical device which is prone to failure.

Even though technological advances have provided surgeons and patients a much wider array of treatment options, the mainstay of treatment of hydrocephalus remains the CSF shunt. Most CSF shunts function by diverting CSF from the intracranial ventricle to another body part, most often the peritoneum, where CSF can be absorbed. Early CSF shunts were not flow regulated, resulting in erratic flow rates and resulting complications. Modern shunts have an intervening valve system that regulates the flow of CSF, reducing the problems of over- and under-drainage that result from the gravitational effects of postural changes. Since the first valved shunt device was implanted in 1949, innumerable ingenious and useful modifications of shunt valve design have been developed in an effort to maintain an intracranial pressure that provides optimal symptom relief while minimizing complications.

Despite these technological advances, CSF shunt failure is still common, with two-thirds of all shunts implanted requiring at least one revision within 10 years of implantation. CSF shunts can fail for a number of reasons, including misplacement, infection, or mechanical failure. Mechanical failure commonly results from blockage, kinking, or breaking of the shunt tubing, resulting in raised intracranial pressure that requires surgical revision. Complete valve blockage can also occur, but symptoms of over- and underdrainage resulting in neurological symptoms is a much more common form of valve malfunction. These flow-related neurological symptoms can have serious detrimental effects.

Most technologic efforts to improve shunt patency and flow-related symptoms have been directed toward the design of a valve that will maintain an intracranial pressure (ICP) that is ideal for each individual in all positions and circumstances. Hundreds of valves have been developed over the past 50 years, with most technological variations focusing on the regulation of CSF flow. Valves manufactured during the first half century of development were of a fixed pressure, meaning that they were made to try to maintain a certain pressure at all times. Each of these valve types were manufactured for various pressure thresholds, realizing that the ideal pressure often varies by patient age, size, and the ventricular size. Unfortunately, predicting the ideal valve for an individual proved difficult, particularly in the growing pediatric patient. Because each implanted valve had a set, fixed pressure, changing the valve required a surgical procedure with all of its inherent risks.

Programmable valves were developed to personalize flow and pressure characteristics of the CSF shunt without the need for an operation to replace the

Date: 4/19/2016 V.2

Principal Investigator: [name]

Application Number: IRB00093490

## JHM IRB - eForm A – Protocol

valve. These valves were designed to be adjustable using magnetic devices applied to the patient's skin. The application of a simple magnetic device to the skin's surface allows a quick and painless way to adjust the pressure settings—an appealing and much less risky alternative to an operation.

### *CSF shunting with Programmable Valves*

The conceptual appeal of programmable valves has led to its widespread use in the developed world for over 15 years, with dozens of technological variations marketed and adopted by surgeons. The Codman Hakim valve (Depuy Synthes, West Chester, PA) and the Strata valve (Medtronic, Ireland) are the most commonly implanted programmable CSF shunt valves worldwide, with Strata valves more commonly implanted by pediatric neurosurgeons in the United States.

Pediatric neurosurgeons' initial clinical experience with programmable valves confirmed the theoretical advantages of quick and painless transcutaneous adjustment of CSF shunt flow and pressure. Korinth *et al.* found that transcutaneous adjustments of valve pressure in neonates allowed greater flow during initial wound healing, which led to less operations and possibly lower infection rates. Kondageski *et al.* found fewer problems with over drainage with programmable valves, while Jallo *et al.* and other authors found a reduction in the need for shunt revision when programmable valves were utilized.

Surgeons' enthusiasm for the use of these intuitively appealing programmable shunts has been tempered by larger studies with longer follow-up, as well as inherent technical problems with the valves themselves. In some series, the use of programmable valves did not reduce shunt revision rates, while others found that the use of programmable valves was actually associated with an increased rate of reoperation. Two randomized controlled trials failed to demonstrate a difference in the need for shunt reoperation based on whether a programmable or fixed pressure valve was inserted.

Programmable valves, having more components and moving parts than fixed pressure valves, have also been found to be more prone to mechanical failure. Studies have shown that programmable valves are more likely to jam, crack, or break, and they may be associated with more skin breakdown because they can have a higher profile than many fixed-pressure valves. Because most programmable valves are adjusted by applying a rotating magnetic field directly over the device, their setting is often affected by the large magnetic field of an MRI study. This MRI susceptibility, coupled with the fact that MRI is the

Date: 4/19/2016 V.2  
Principal Investigator: [name]  
Application Number: IRB00093490

## JHM IRB - eForm A - Protocol

diagnostic study of choice to assess shunt function, leads to mandatory valve checks by health care providers after each and every MRI study.

Programmable valves are more prone to mechanical failure, and require an added burden for providers and parents. Even so, they are still widely utilized by clinicians worldwide. Surgeons question the validity of published research on this topic, with most studies reporting class II or III data. Even the applicability of the randomized controlled trial data regarding programmable valves has been questioned because of significant patient heterogeneity and a limited sample size. Many surgeons believe that the intuitive theoretical advantages of the programmable valve may be useful for a subset of patients, particularly young infants, patients with very large ventricles or patients who seem to be particularly sensitive to variations in intracranial pressure.

## JHM IRB - eForm A – Protocol

Device	Notes
iPad 	Magnetic cover may increase risk
Headphones 	Bose > Beats, Earbuds
Magnetic toys 	A wide variety, small and large
Cell phone 	Particularly smartphones
Handheld portable games 	Nintendo DS
Vagus nerve stimulator magnet 	Patients with shunts can also have VNS
Transcranial magnetic stimulation 	
Cordless drill 	
Close contact with television 	Direct contact
Amusement park rides 	Magnetic fields or gravitational forces
Direct trauma to valve 	
Magnetic Induction therapy devices 	Prominent in Japan

The frequency with which programmable valves become inadvertently reset as a result of environmental exposure has not been systematically studied and is largely unknown. A literature review by the FDA in 2012, as well as a more recent exhaustive review by our study group, failed to identify a study that carefully evaluated a population of patients with CSF shunts to define the prevalence of inadvertent valve reprogrammings, regardless of symptoms. However, other small studies have clearly shown that IR does occur.

Most previous studies point to IR discovered during clinical evaluations for possible shunt malfunction, not evaluating each patient systematically regardless of their clinical status. Kestle *et al.* found that the Strata valve had an “unexplained change in performance level” 25 times in a total of 22 patients in their 315-patient multicenter study. More recently, Kondageski *et al.* from Great Ormond Street Hospital found that 7 of 24 (29%) patients closely followed with programmable valves were found to have had IR: two were believed to have been related to trauma and 5 had no identifiable cause. Other less comprehensive studies, which likely reported only accidental reprogrammings that were discovered when a shunt malfunctioned, reported IR in 0% and 10% of patients.

Because IR may not cause symptoms severe enough to prompt clinical and/or radiographic evaluation, the lack of a systematic study leaves the true prevalence unknown. IRs have repeatedly been shown to cause symptoms of

Date: 4/19/2016 V.2  
Principal Investigator: [name]  
Application Number: IRB00093490

## JHM IRB - eForm A – Protocol

over- or underdrainage, requiring valve reprogramming or surgery for replacement. One patient was reported to have attempted suicide by deliberately reprogramming his shunt valve using a handheld degausser. Fortunately, there are no known cases of death that have resulted from IR to date.

The concurrent proliferation of magnetically programmable CSF shunt valves and household devices containing magnets led to a recent FDA warning and recommendation related to IR of CSF shunt valves. In its 2014 report, the FDA deemed programmable valves safe and did not advise patients to avoid using specific electronic devices or magnets. Based on its identification of 83 non-MRI related IRs of programmable valves in the literature, and its independent study of the field strengths of commonly used household devices, the FDA did, however, make recommendations regarding the way household products are used in patients with programmable CSF shunt valves. The agency qualified its recommendations based on future testing, but at this time it has recommended that household items with potential magnet fields be kept at least two inches from adjustable CSF shunt valves.

Growing concern among patients and parents of children with programmable valves has led to U.S. patent applications for devices to help shield these valves from magnetic fields and to the establishment of companies to sell headbands and hats to provide a magnet shield for programmable valves.

Manufacturers continue their efforts to design shunt valves that are less sensitive to magnetic fields. However, most of these MRI-resistant devices have not been widely adopted. If and when safer programmable valves are developed and widely implanted, patients and surgeons will be forced to debate the necessity of replacing the old MRI-susceptible valves with newer valves that are less likely to be inadvertently reprogrammed. The implications of such a decision are not trivial, because even a simple operation to change a CSF shunt valve carries most of the usual risk of shunt surgery. Having knowledge of the true prevalence and implications of IR will help patients and health care providers make better decisions about the necessity of changing a CSF shunt valve when newer, safer models are widely available.

### *Study Objectives*

We intend to systematically study our patient population with magnetically susceptible programmable shunts to define the prevalence and consequences of IR, which will enable patients and health care providers to make more informed decisions about the importance of avoiding magnetic fields in household devices

Date: 4/19/2016 V.2  
Principal Investigator: [name]  
Application Number: IRB00093490

## **JHM IRB - eForm A – Protocol**

and the necessity of surgery to replace a magnetically susceptible CSF valve to a different version that is less likely to inadvertently reprogram.

### **4) Study Procedures**

#### *Participants*

Patients 21 years of age and younger, with Strata valve CSF shunts, who are being evaluated by the All Children's Hospital (ACH) neurosurgical service as part of standard of care, will be eligible for participation during the three-year enrollment period. Each time an eligible patient has contact with the neurosurgical service their valve will be checked for possible inadvertent reprogramming in the outpatient facilities, emergency department, and inpatient setting. Patients will have their valves checked as part of this study during each encounter. Only patients who were evaluated by the neurosurgical service and returned to their normal environment more than seven days prior to their current encounter will be eligible to have their valves rechecked as part of this study.

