#### *Eligible Participants and Consent*

Evaluating IR and making correlations between exposure to MRI or environmental magnets and symptoms and radiographic changes (when available) will require the patient or family to complete a brief questionnaire. It will then require the study team and delegated providers to check the valve setting before and after MRI, and to gather clinical information from the medical record and from the current clinical evaluation.

Each patient's initial enrollment will require the acquisition of an informed consent, which will cover all future evaluations of IR during the three year study period for that patient. However, every time a patient enrolled in the study encounters the neurosurgical service, all study steps will be performed, including the valve check before and after MRI, the participant's completion of the questionnaire, and the research staff's completion of the data sheets.

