### **5) Inclusion/exclusion**

All patients with a Strata valve CSF shunt, who are 21 years of age or younger, will have the option to participate in this study. Patients who are over 21, those without a Strata valve CSF shunt, or those patients in whom the Strata valve is not checked prior to MRI scanning will be ineligible for the study. In addition, only patients who were evaluated by the neurosurgical service and returned to their normal environment more than seven days prior will be eligible to have their valves rechecked as part of this study.

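### The seven-day rule on study rechecks has no exemption for before-and-after MRI readings, so it conflicts with the every-encounter instruction and would discard valid repeat pairs for Aim 2

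*Combined protocol and SAP*

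**What the plan says.** Four places in the protocol bear on when a valve is read for the study.

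- **Section 4, Participants.** It first states: "Patients will have their valves checked as part of this study during each encounter". The next sentence restricts this: "Only patients who were evaluated by the neurosurgical service and returned to their normal environment more than seven days prior to their current encounter" may have a study recheck. No aim is named and MRI readings are not exempted.
- **Section 5, Inclusion/exclusion.** The limit is repeated as a criterion: "only patients who were evaluated by the neurosurgical service and returned to their normal environment more than seven days prior will be eligible" for a recheck. Again it is not limited by aim.
- **Section 4, Eligible Participants and Consent.** One consent covers the whole study period, and "every time a patient enrolled in the study encounters the neurosurgical service, all study steps will be performed". The readings on both sides of an MRI are named among those steps. No seven-day limit appears.
- **Section 2, Objectives.** Valve settings are to be read before and after any MRI. Aim 2 asks: "does the field strength of MRI scanning correlate with the likelihood that the shunt valve will change during the MRI study".

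Under Statistical Considerations, Aim 2 is analysed with generalized estimating equations (GEE) that allow for several evaluations per child.

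**The concern.** A week back home makes sense when the question is whether something in the child's surroundings moved the valve, because the child needs time to be exposed. Aim 2 asks a different question. Its outcome is the difference between a reading just before the scan and one shortly after, both taken in one encounter. The interval since the last visit has no bearing on whether that pair is valid.

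Two things are at stake. First, a repeat scan soon after a visit, or a second scan in the same admission, would add information to the 3T versus 1.5T comparison and is lost if the restriction is followed. The loss is permanent. The section on burden to families says valve checks at every MRI are already current practice and that the pre-scan check is what the study adds. If that reading is skipped, routine records may not supply the baseline. Second, staff working from the consent section would collect these pairs and staff working from the eligibility section would not, so the data set would depend on which section was followed.

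**Working it through.** No figure in the plan depends on the seven-day rule, so there is no stated number to reproduce. The check is a comparison of the sections, case by case.

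**Cases**

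1. *Enrolled child, evaluated, sent home, scanned more than seven days later.* All sections agree that the pair is taken.
2. *Enrolled child, evaluated, sent home, scanned on day 4.* Participants and Inclusion/exclusion: not eligible for a recheck, so no pair. Consent section and Objectives: pair taken. **Conflict.**
3. *Enrolled inpatient, second MRI in the same stay.* The child has not returned to the normal environment, so Participants and Inclusion/exclusion give no pair. Consent section and Objectives: pair taken. **Conflict.**
4. *Newly enrolled child, first study check, with MRI.* The restriction concerns rechecks, so on a plain reading this pair is taken. Some ambiguity remains: Sequence of Evaluations also calls the post-scan reading a recheck, and Inclusion/exclusion lists the rule among the eligibility criteria.

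**Can the conflict be read away?** Within Participants it can: the restrictive sentence follows the each-encounter sentence and may qualify it. The consent section carries no such qualifier and lists the MRI readings by name.

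**Does the rule serve Aim 2?** Objectives defines the Aim 2 question as change during the scan. Statistical Considerations says only that the outcome is reprogramming present or absent; I take this to mean change across the scan, as Objectives asks. On that basis, time at home plays no part. Repeated pairs from one child are no obstacle, because the planned GEE allows for them.

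**How large is the loss?** It cannot be computed. The documents give no number of MRIs, no split between 3T and 1.5T, no share of scans within seven days or in the same stay, and no power for Aim 2. Sample Size Estimation is based on the device association (Aim 4). Its assumption of at least three evaluations per patient on average says nothing about their spacing.

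Purely as arithmetic, if a share f of pairs were lost and pairs were independent, the confidence interval for the log odds ratio would widen by 1/sqrt(1 - f):

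- f = 5%: 1/sqrt(0.95) = 1.03
- f = 10%: 1/sqrt(0.90) = 1.05
- f = 20%: 1/sqrt(0.80) = 1.12
- f = 30%: 1/sqrt(0.70) = 1.20

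These values of f are assumptions with no basis in the documents. Independence is also doubtful, since the lost pairs are repeats in children who usually already contribute one. With positive within-child correlation and repeats at the same field strength, the formula overstates the loss. The list shows how precision would respond and does not estimate this study's loss.

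**The case against.** The strongest reply is that this is a drafting gap of narrow reach. The rule governs rechecks, while entry is set separately and includes the inpatient setting. The consent sentence explains that consent is taken once while procedures repeat, and merely omits the limit stated just before it. Few scans may be affected, and no Aim 2 target exists against which to show a shortfall. Counting every rapid repeat scan also gives more weight to children who are scanned often, so including those pairs is partly a matter of preference.

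Much of this stands. The reach is narrow, the loss is unknown and the weighting point is fair. What does not fall away is that the rule names no aim, the consent section is unqualified, and a repeat pair within seven days is a valid Aim 2 observation that one set of instructions collects and another discards.

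A reader might infer more, and the documents do not support it:

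- *That the rule bars every study check, including those of children new to the service or the first scan of a newly enrolled inpatient.* A first check is not, on a plain reading, a recheck.
- *That Inclusion/exclusion contradicts itself by opening the study to all patients with the valve.* That sentence concerns the option to take part. A general offer followed by a restriction is ordinary drafting.
- *That the field-strength comparison is biased.* This would require short-interval scans to go more often to one scanner strength, and nothing in the documents says so.

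**Conclusion.** The point holds in a limited form. For already enrolled children with a repeat MRI within seven days or in the same stay, the sections contradict each other, and the restrictive ones discard before-and-after pairs that are valid for Aim 2. This rests on reading Aim 2's outcome as change during the scan and on reading the rule as written, without an implied exemption for MRI.

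The documents do not allow the size to be stated, and it would be wrong to report a percentage loss of precision or a shortfall for Aim 2. The case for acting is that an omitted pre-scan reading may not be recoverable later, whereas an unneeded one can be left out of an analysis.

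**What to change.** 1. In Participants and Inclusion/exclusion, limit the seven-day, normal-environment condition to the analyses of reprogramming between encounters (Aims 1, 3 and 4).
2. State that every MRI with a reading before and after it counts for Aim 2, whatever the interval since the last encounter, with repeated pairs from one child handled by the planned GEE.
3. Align the consent section with this, so that all sections describe the same set of checks.
4. Flag short-interval and same-stay encounters in the database, so that they are kept for Aim 2 and left out of the environmental-exposure analyses.

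The cost is protocol wording, one database field, a few extra data sheets and valve checks of 5-15 seconds each. No extra scan is needed, because these children are being scanned as part of their care. The drawback is somewhat more weight on frequently scanned children in Aim 2. A sensitivity analysis without the flagged pairs would show whether that matters.
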